5.2 General Concomitant Medication and Supportive Care Guidelines

Capecitabine (Xeloda) and Coumadin

Capecitabine (XELODA) Warfarin Interaction: Patients receiving concomitant capecitabine and oral coumarin-derivative anticoagulant therapy should have their anticoagulant response (INR or prothrombin time) monitored frequently in order to adjust the anticoagulant dose accordingly. A clinically important XELODA-Warfarin drug interaction was demonstrated in a clinical pharmacology trial. Altered coagulation parameters and/or bleeding, including death, have been reported in patients taking XELODA concomitantly with coumarin-derivative anticoagulants such as warfarin and phenprocoumon. Postmarketing reports have shown clinically significant increases in prothrombin time (PT) and INR in patients who were stabilized on anticoagulants at the time XELODA was introduced. These events occurred within several days and up to several months after initiating XELODA therapy and, in a few cases, within one month after stopping XELODA. These events occurred in patients with and without liver metastases. Age greater than 60 and a diagnosis of cancer independently predispose patients to an increased risk of coagulopathy.

Bone Metastases: For patients with documented bony metastases, treatment with zolendronic acid, pamidronate or denosumab per standard UWCCC protocol is recommended.

Nausea/Emesis: Patients must be counseled on the use of antiemetics for treatment of nausea and vomiting with a standard antiemetic regimen (for example, prochlorperazine 10 mg orally every 6 hours as needed for nausea, or lorazepam 0.5 mg orally every 4 hours as needed for nausea). Any patient who is vomiting medications or pill fragments should be instructed NOT to repeat dosing. If nausea or emesis leads to the patient feeling lightheaded or dizzy or unable to stay hydrated at home should be instructed to seek medical attention.

Colony Stimulating Factors: CSFs should not be used during the first course of therapy and should not be used subsequently unless there are significant medical circumstances that require CSFs. Use of any CSFs must be discontinued at least 24 hours prior to initiation of the next cycle of chemotherapy and must be documented in the patient record.

Diarrhea: Patients should be instructed prior to cycle 1, day 1 in the proper use of antidiarrhea agents (such as loperamide [Imodium AD]). For example, with loperamide [Imodium AD], instruct patients to take 4 mg (2 capsules) after the first loose stool of the day, and 2 mg each loose stool thereafter. 4 mg may be taken every 4 hours overnight. Instruct the patient to stop taking the Imodium when they have not had a bowel movement for 12 hours. Total daily dose should not exceed 16 mg. Patients should be instructed to call for any diarrhea not improved by Imodium.

5.3 **Duration of Therapy**

In the absence of treatment delays due to adverse event(s), treatment may continue until one of the following criteria applies:

- Disease progression.
- Intercurrent illness that prevents further administration of treatment.
- Unacceptable adverse event(s).
- Patient decides to withdraw from the study or is unevaluable after cycle 1.
- General or specific changes in the patient's condition render the patient unacceptable for further treatment in the judgment of the investigator.
- Treatment delay greater than 2 weeks

5.4 **Duration of Follow Up**

All patients enrolled in the study will be followed until both of the following criteria are met:

1. Study drug is discontinued (for any reason)

2 All study drug related adverse events have either resolved to grade 1 or stable per the discretion of the treating physician.

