1. OBJECTIVES

1.1. **Primary Objective**: To characterize the effect on pharmacokinetic parameters of capecitabine, when dosed using actual versus ideal body weight in obese patients with advanced solid tumors.

1.2. Secondary Objectives:

1.2.1 To characterize the response rate and progression free survival with capecitabine therapy in obese subjects with advanced solid tumors

1.2.2 To determine capecitabine pharmacokinetics in obese patients compared with normal weight historical controls.

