5.5 Criteria for Removal from Study

Patients will be removed from study when any of the criteria listed in Section 5.3 applies. The reason for study removal and the date the patient was removed must be documented in the Case Report Form.

5.6 **Definition of Evaluable Patients**

Patients will be evaluable for the primary endpoint if he or she takes 100% of their capecitabine dose days 1 through 9 and at least 90% of their capecitabine dose days 10 through 15 in cycle one. Unevaluable patients will go off study after cycle 1, but may continue to be treated with commercial capecitabine per the discretion of the treating physician.

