11.1.4.3 Evaluation of Best Overall Response

The best overall response is the best response recorded from the start of the treatment until disease progression/recurrence (taking as reference for progressive disease the smallest measurements recorded since the treatment started). The patient's best response assignment will depend on the achievement of both measurement and confirmation criteria at least 4 weeks after initial response is documented.

Target	Non-Target	New	Overall	Best Response for this
Lesions	Lesions	Lesions	Response	Category Also Requires:
CR	CR	No	CR	\geq 4 wks. confirmation
CR	Non-CR/Non-	No	PR	
	PD			\geq 4 wks. confirmation
PR	Non-PD	No	PR	
SD	Non-PD	No	SD	documented at least once ≥ 4
				wks. from baseline
PD	Any	Yes or No	PD	
Any	PD*	Yes or No	PD	no prior SD, PR or CR
Any	Any	Yes	PD	
* In excepti	onal circumstances	, unequivocal p	progression in	non-target lesions may be
accepted a	as disease progressi	on.		

Note: Patients with a global deterioration of health status requiring discontinuation of treatment without objective evidence of disease progression at that time should be reported as "*symptomatic deterioration*." Every effort should be made to document the objective progression even after discontinuation of treatment.

11.1.5 **Duration of Response**

Duration of overall response: The duration of overall response is measured from the time measurement criteria are met for CR or PR (whichever is first recorded) until the first date that recurrent or progressive disease is objectively documented (taking as reference for progressive disease the smallest measurements recorded since the treatment started).

The duration of overall CR is measured from the time measurement criteria are first met for CR until the first date that recurrent disease is objectively documented.

Duration of stable disease: Stable disease is measured from the start of the treatment until the criteria for progression are met, taking as reference the smallest measurements recorded since the treatment started.

11.1.6 Progression-free survival:

Progression-free survival (PFS) will be defined as time from first dose of capecitabine to time to clinical or imaging evidence of progressive disease.

11.1.7 **Response Review**

The imaging for any subjects obtaining a CR or PR will be reviewed centrally at the University of Wisconsin by an independent investigator.

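### Sections 5.4 and 5.5 provide no systematic follow-up for progression after a patient stops capecitabine or leaves the study without progression, although PFS is a secondary endpoint defined to progression

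*Combined protocol and SAP*

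**What the plan says.** Objective 1.2.1 is "To characterize the response rate and progression free survival with capecitabine therapy in obese subjects with advanced solid tumors". Section 11.1.6 runs PFS from the first dose to clinical or imaging progression, with no restriction to time on treatment. Section 13.4 applies Kaplan-Meier and gives no censoring rule.

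On follow-up, Section 5.4 states: "All patients enrolled in the study will be followed until both of the following criteria are met". The first criterion is "Study drug is discontinued (for any reason"); the second is "All study drug related adverse events have either resolved to grade 1 or stable per the discretion of the treating physician". Progression appears in neither.

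Section 5.3 lists several reasons for stopping other than progression, among them intercurrent illness, unacceptable toxicity, a change in condition and a delay of more than 2 weeks. Section 5.5 then says: "Patients will be removed from study when any of the criteria listed in Section 5.3 applies". Section 6 adds further exits, for grade 4 haematologic toxicity, for repeated hand-foot reaction and for needing more than 2 dose reductions. Section 5.6 adds another route: "Unevaluable patients will go off study after cycle 1, but may continue to be treated with commercial capecitabine".

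The Section 10 calendar marks tumor measurements at Off Study and has no column after it. The note in 11.1.4.3, written for patients who stop because of global deterioration without objective progression, points the other way: "Every effort should be made to document the objective progression even after discontinuation of treatment".

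**The concern.** The endpoint needs a progression date for each patient, or a censoring time unrelated to prognosis. A patient who stops for toxicity, delay or intercurrent illness has, by definition, not progressed at that time. The Off Study assessment then normally supplies a censoring time rather than an event, and the plan schedules nothing later.

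Kaplan-Meier treats a censored patient as carrying the same future risk as those still under observation. If those who stop are on average closer to progression, the curve is too high. A different censoring rule cannot make good dates that were not collected.

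The Section 5.6 route matters too. Those patients leave at about week 3, before the one response assessment that Section 11.1 requires, at 6 to 9 weeks. They may have no post-baseline tumor assessment except the one at Off Study.

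**Working it through.** **The plan's own figures.** The plan gives no event count, precision or power for PFS. Its n = 10 comes from the PK comparison. Exact paired-t power (difference 30%, SD 25%, two-sided 0.025, 9 degrees of freedom) is 84.2% at n = 10, and 10 is the smallest n that reaches 80%, as Table 13.1 shows. This says nothing about PFS.

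**What each provision yields after an exit without progression.**

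| Provision | Progression information |
|---|---|
| Calendar, Off Study column | One tumor assessment at exit |
| 5.4, both criteria required | Follow-up may outlast dosing until toxicity settles; no tumor assessment attached |
| 11.1.4.3 note | Progression to be sought, for symptomatic deterioration only; no schedule or data route |
| 11.1.6 | Clinical progression counts, so a decline judged to be progression is an event at once |
| 5.6 | Off study after cycle 1, possibly still on drug; nothing further scheduled |

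None of these gives systematic follow-up to progression.

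**Size, on assumed inputs.** The documents give no stopping rate, no median PFS and no link between stopping and progression. I assume:

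- PFS is exponential with a 4-month median, so λ = ln 2 / 4 = 0.1733 per month.
- A 30% subgroup has hazard kλ, and each member is assigned a stop time u, uniform from 0.7 to 3 months.
- Members who have not progressed by u are censored there.

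True curve: S(t) = 0.7·exp(−λt) + 0.3·exp(−kλt).

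Let G(t) be the chance that the stop time is later than t: 1 up to 0.7 months, (3 − t)/2.3 up to 3 months, then 0. In large samples Kaplan-Meier tends to exp(−∫h), with

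h(t) = [0.7·exp(−λt)·λ + 0.3·exp(−kλt)·G(t)·kλ] / [0.7·exp(−λt) + 0.3·exp(−kλt)·G(t)].

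Share censored without progression = 0.3 × [exp(−0.7kλ) − exp(−3kλ)] / (2.3kλ). At k = 2 this is 0.3 × (0.7846 − 0.3536)/0.797 = 0.162.

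| k | True median (months) | KM median (months) | True 6-month PFS | KM 6-month PFS | Dates lost per 10 |
|---|---|---|---|---|---|
| 1 | 4.0 | 4.0 | 35% | 35% | 2.2 |
| 1.5 | 3.5 | 3.7 | 31% | 34% | 1.9 |
| 2 | 3.2 | 3.5 | 28% | 32% | 1.6 |
| 3 | 2.8 | 3.1 | 26% | 30% | 1.2 |

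Fewer than 3 of 10 dates are lost because some of the 30% progress before their assigned stop.

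**A second model.** Let a share s of patients stop before progressing, and let the hazard rise k-fold only after the stop. In units of the on-drug hazard, with h = s/(1 − s), true S(t) = exp(−(1+h)t) + h·[exp(−kt) − exp(−(1+h)t)]/(1 + h − k), while Kaplan-Meier estimates exp(−t). For s from 10% to 50%, expected events fall from 10 to between 9 and 5. The median is overstated by 0% at k = 1, by 3% to 21% at k = 2 and by 5% to 34% at k = 3. At s = 30% the figures are 10% and 17%.

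**The case against.** A reader might infer that progression after such a stop is never observed, or that PFS is in effect measured only on drug. The documents do not support either reading. Tumor measurements are marked at Off Study. Section 5.4 needs both criteria, so follow-up can outlast dosing. The 11.1.4.3 note asks for progression after discontinuation in one group, and the tension with 5.4 and 5.5 is confined to that group. Section 11.1.6 accepts clinical progression, so some stops for decline will be events. Conversely, under 5.6 a patient can leave the study while still taking capecitabine, so time observed is not the same as time on drug.

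A reader might also infer that the loss is beyond repair. Routine-care records may allow later recovery, if consent covers it; the consent form was not available to check.

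The strongest objection is about scale. PFS is descriptive, across mixed tumor types, in a 10-patient PK pilot. At k = 2 in the first model, the Kaplan-Meier median from 10 patients ranges from about 1 to 9 months (2.5th to 97.5th percentile), and from about 1 to 7 months with complete follow-up. A shift of 0.3 months is small against that. The prognostic link is itself an assumption: with none there is no bias, and if those who stop did better than the rest the bias would reverse.

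All of this limits the size of the point. It does not remove the gap: a site that follows 5.4 and 5.5 as written has no instruction to collect dates that a stated objective needs.

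**Conclusion.** The point holds as a gap in data collection and an inconsistency between sections. After an exit without progression, including the 5.6 exits, the plan collects progression only at the Off Study assessment and incidentally while toxicity settles. Sections 5.4 and 5.5 need to be reconciled with 11.1.4.3 and with the PFS definition in 11.1.6.

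Censoring at these exits may be informative. In the first model the median is overstated by 0 to about 0.3 months, and about 1 to 2 of 10 patients lose a progression date. The second model spans 0 to 34% over a wider range of stopping rates. Every input is assumed, so these figures illustrate the problem and do not predict its size. If stopping is unrelated to prognosis, the only cost is lost events. The primary PK comparison uses cycle 1 data and is unaffected. The point is minor to moderate, and worth acting on because the remedy is cheap.

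**What to change.** Amend 5.4, 5.5 and the Section 10 calendar, and align them with 5.6 and 11.1.4.3. Leaving study treatment should end study visits, not collection of the PFS outcome. For every patient who stops capecitabine or leaves the study without progression and has not withdrawn consent, record these by chart review of routine care:

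- progression status and date;
- date of death;
- start of any other anticancer therapy.

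Add a post-study follow-up column to the calendar for this. Collection should continue past the start of another therapy, so that a switch does not become a new point of loss.

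In 11.1.6 and 13.4, state whether death is a PFS event, how new anticancer therapy is handled, and when patients without an event are censored.

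Cost: a short amendment, a check that consent covers the chart review, a little chart review for the few patients concerned, and somewhat later database closure for the secondary endpoint. No scans or visits are added, and the treatment and stopping rules are untouched.

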3.2 Exclusion Criteria

- 3.2.1 Patients who have had systemic chemotherapies or targeted therapies within 3 weeks or radiotherapy within 2 weeks prior to entering the study or those patients whose adverse events from prior therapies have not recovered to \leq grade 1 (other than grade 2 neuropathy, lymphopenia and alopecia which are permitted.)
- 3.2.2 Patients receiving any other investigational agents for cancer treatment.
- 3.2.3 Patients with treated, stable brain metastases are allowed to enroll. Patients must be at least 4 weeks from brain radiation and off any medications used to treat brain metastases including steroids. Patients are allowed to be on anti-epileptic medications that are not contraindicated as listed in Appendix C.
- 3.2.4 Patients with any condition of the gastrointestinal tract that is expected to result in an inability to swallow or absorb oral medications (ie. prior surgical procedures affecting absorption and requiring i.v. alimentation). This will be determined at the discretion of the PI.
- 3.2.5 Patients may not be taking any concomitant drugs that are contraindicated based on the drug-interaction table in Appendix C.
- 3.2.6 Concurrent treatment with warfarin (coumadin) is allowed, but close monitoring of the PT/INR is recommended.
- 3.2.7 Uncontrolled intercurrent illness including, but not limited to, ongoing or active severe infection, symptomatic congestive heart failure, unstable angina pectoris, clinically significant or symptomatic cardiac arrhythmia, other malignancies requiring therapy or psychiatric illness/social situations that would limit compliance with study requirements.

- 3.2.8 Pregnant women or women who are breastfeeding are excluded from this study because capecitabine is a pregnancy category D drug and is known to pass to the infant in breastmilk.
- 3.2.9 Patients with known deficiency of the dihydropyrimidine dehydrogenase (DPD) enzyme.
- 3.2.10 History of allergic reactions attributed to compounds of similar chemical or biologic composition to capecitabine.

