Depending on the nature, severity, and attribution of the serious adverse event an SAE report will be phoned in, submitted in writing, or both according to the table below. All serious adverse events must also be reported to the UWCCC Data and Safety Monitoring Committee Chair. All serious adverse events must also be reported to the UW IRB (if applicable), and any sponsor/funding agency not already included in the list.

Determine the reporting time line for the SAE in question by using the following table.

SAE Requiring 7 Day Reporting Occurs at UWCCC:

1. **Report to the UWCCC:**

Reference the **SAE SOP** and the **SAE Reporting Workflow for DOWGs** on the UWCCC website (http://www.uwccc.wisc.edu) for specific instructions on how and what to report to the UWCCC for 7 day reports.

For this protocol, the following entities are required to be notified:

- a) [contact]
- b) Any appropriate parties listed on SAE Routing Form

2. **Report to the IRB:**

Consult the UW-IRB website for reporting guidelines.

3. **Reporting to the FDA**

Serious Adverse Events occurring on studies on which a UW PI is acting as sponsor-investigator must be reported to the FDA within the appropriate time frame. Mandatory and voluntary reporting guidelines and instructions are outlined on the FDA website: http://www.fda.gov/Safety/MedWatch/HowToReport/default.htm

Report the SAE using the FDA Med Watch form available at http://www.fda.gov/downloads/Safety/MedWatch/HowToReport/DownloadForms/UCM082728.pdf.

Expedited reporting requirements for adverse events experienced by patients on arm(s) with						
commerciara	agents only—Arms	I, А, Б, апо С. do 4	Grado 5ª			
Attribution	Gia	ue 4	Graue	5.0		
Auribution	Unexpected	Expected	Unexpected Expected			
	Unexpected	Expected	Olicypeeted	Expected		
Unrelated or Unlikely			7 calendar days	7 calendar days		
Possible, Probable, Definite	7 calendar days		7 calendar days	7 calendar days		
7 Calendar I	Days: Indicates a f	ull MedWatch repor	rt is to be submitted v	within 7 calendar days		
of learning of	f the event.					
a This incluc	les all deaths withir	n 30 days of the last	dose of treatment re	egardless of attribution.		
NOTE: Any death that occurs > 30 days after the last dose of treatment and is attributed possibly, probably, or definitely to the treatment must be reported within 7 calendar days of learning of the event.						

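### Section 5.4 sets no minimum safety follow-up after the last capecitabine dose, although every death within 30 days of that dose is reportable

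*Combined protocol and SAP*

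**What the plan says.** Section 5.4 states: "All patients enrolled in the study will be followed until both of the following criteria are met". The first criterion is that the drug has been stopped, for whatever reason. The second is "All study drug related adverse events have either resolved to grade 1 or stable per the discretion of the treating physician". No number of days is attached to either. Section 5.5 adds: "Patients will be removed from study when any of the criteria listed in Section 5.3 applies". The criteria in Section 5.3 include progression, unacceptable adverse events, withdrawal by the patient and a treatment delay of more than 2 weeks.

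The calendar in Section 10 ends with an Off Study column. It includes an adverse event evaluation, concurrent medications, physical exam, blood count and chemistries. The column has no day or window, and no column follows it. PT/INR appears in no row.

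The expedited reporting table in Section 7.3 looks further ahead. Its footnote takes in all deaths within "30 days of the last" dose, regardless of attribution. A note extends the duty to "Any death that occurs > 30 days after the last dose of treatment and is attributed possibly, probably, or definitely to the treatment". The 7-calendar-day clock starts when the site learns of the event.

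Section 5.2 discusses coumarin anticoagulants. It reports raised PT and INR after capecitabine was started and, "in a few cases, within one month after stopping XELODA". Such patients can enter under Section 3.2.6: "Concurrent treatment with warfarin (coumadin) is allowed, but close monitoring of the PT/INR is recommended".

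**The concern.** The plan states how long after the last dose a death matters (30 days, whatever the cause) and how late one known interaction has been seen (about a month). It then defines an end of follow-up that can come before either period has run. A patient who stops with no active related event, or only stable ones, meets both conditions of Section 5.4 on the day of stopping.

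A duty to report does not find events. Because the clock runs from the moment of learning, a death or bleed that nobody looked for breaches no deadline and enters no report. The setting makes this more than theoretical: patients have advanced cancer, the eligibility floor for life expectancy is 12 weeks (Section 3.1.6), and progression is a listed reason to stop. The summary reports to the DSMC can contain only what the site has learned. With a planned 10 patients, one unrecorded death or bleed would be a visible share of the safety record.

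**Working it through.** The plan gives no figure for follow-up after the last dose, so there is nothing to reproduce. The check is a day count against the plan's own windows.

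**Inputs**
- Death-reporting window: 30 days from the last dose (Section 7.3, table footnote).
- Post-stopping window for the coumarin interaction: one month (Section 5.2).
- Last planned dosing day: day 15 in cycle 1, day 14 in later cycles (Section 5.1).
- Cycle length 21 days, so the next planned day 1 falls on day 22 of the current cycle.
- Longest delay before removal: 2 weeks, or 14 days (Sections 5.3 and 6.1).
- Minimum interval required by Section 5.4: none, so 0 days.

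**Formulas**
- Days since last dose at exit = (day of exit) − (day of last dose).
- Days left uncovered = 30 − days since last dose at exit.

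| Exit point | Days since last dose | Days of 30 uncovered |
|---|---|---|
| Stops during dosing, no active or only stable related events | 0 | 30 − 0 = 30 |
| Next planned day 1, after cycle 1 | 22 − 15 = 7 | 30 − 7 = 23 |
| Next planned day 1, after cycle 2 or later | 22 − 14 = 8 | 30 − 8 = 22 |
| After a full 2-week delay, following cycle 1 | 7 + 14 = 21 | 30 − 21 = 9 |
| After a full 2-week delay, following cycle 2 or later | 8 + 14 = 22 | 30 − 22 = 8 |

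The last four rows assume that dosing ran to the last planned day. A dose held earlier in the cycle moves the last dose back and lengthens the interval at the same exit. The table therefore shows ordinary exits and sets no ceiling. What Section 5.4 guarantees is the first row: 0 of 30 days.

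**Does another section close the gap?**
- *Section 10, Off Study column:* one real check around exit, but it is undated and nothing comes after it.
- *Sections 3.2.6 and 5.2:* PT/INR monitoring is advised, with no schedule and no stated period after stopping.
- *Section 11.1.4.3:* asks for efforts to document progression after discontinuation in symptomatic deterioration. This does not collect deaths or coagulation events.
- *Sections 11.1.1 and 13.5.1:* say when a patient becomes evaluable for toxicity, not when that ends.

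None supplies a scheduled contact later in the 30 days.

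**The case against.** The strongest reply is that there is no strict contradiction. Section 7.3 says what to report once known, and Section 5.4 says how long to follow. That is fair: this is a gap in active ascertainment, not two rules that cannot both be obeyed. Toxicity is neither an objective nor an endpoint, and the last pharmacokinetic sample is taken on day 15 of cycle 1, so the primary comparison is untouched.

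Several stronger readings are tempting, and the documents do not support them:

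- *That follow-up always ends on the day of stopping.* Both conditions must hold, so a patient with a known, unstable related event is followed longer. Many exits will fall at a planned day 1, 7 or 8 days after the last dose.
- *That nothing is scheduled to detect events.* The Off Study evaluation exists, Section 7.2 has each subject's results discussed at weekly meetings, and Section 7.3 refers to an institutional reporting procedure outside these documents. Usual care may also reveal events. The gap is in what follows the Off Study evaluation.
- *That fatal bleeding is documented up to a month after stopping.* In Section 5.2 the sentence on bleeding and death carries no timing. The one-month remark follows the PT/INR increases and refers most naturally to them.
- *That the interaction figures in Section 2.3 (S-warfarin AUC up 57%, maximum mean INR up 91%, four patients) measure this gap.* They describe giving the drugs together, not risk after stopping.
- *That toxicity totals will be too low.* They could be. The documents give no rate of post-stopping events and no expected number of coumarin users.

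With these readings set aside, the absence of a minimum interval and the empty calendar after exit still stand.

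**Conclusion.** The point holds as a gap in safety ascertainment that is worth closing. Followed exactly, the plan guarantees none of the 30 days over which it makes all deaths reportable. Ordinary exits leave 22 or 23 days uncovered at the next planned day 1, and 8 or 9 after a full 2-week delay. Later deaths, new adverse events and post-stopping PT/INR rises would be captured only passively, and the safety reports could be incomplete for that period.

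This rests on two assumptions: that the Off Study evaluation takes place at exit, since the calendar does not date it, and that no procedure outside these documents requires a later contact. A site that already calls every patient at 30 days would close the gap in practice, but the plan does not ask for it. The number of events missed cannot be estimated from the documents.

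**What to change.** Add a third condition to Section 5.4: that at least 30 days have passed since the last dose of capecitabine given on study. Add one calendar column for a contact at 30 days, by telephone or chart review. It should record vital status, new or worsening adverse events and, for patients on coumarins, bleeding events and any INR results obtained in usual care.

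Three details need settling in the same amendment:

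- Reword Section 5.5 so that removal from study treatment does not end this safety follow-up.
- Apply the contact to every treated patient, including those replaced, unless consent to follow-up is withdrawn.
- Section 5.6 lets unevaluable patients leave the study and continue commercial capecitabine. State which last dose starts their 30 days.

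Thirty days covers the whole death window, and the one-month window to within a day if a month is read as 28 to 31 days. Attributed deaths after day 30 would still be reported only as they become known.

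The cost is one short contact for each of about 10 patients plus replacements, and a close-out about one month later. No blood draw, clinic visit or treatment rule changes.
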